2.3.1.4 General Risk-Mitigation Plan

At this stage of development, the risk mitigation plan for MEDI7352 includes:

- ∀ Implementation of appropriate inclusion/exclusion criteria, baseline evaluations, and restrictions applied during the conduct of the clinical studies, specifically:
 - # Exclusion of concomitant oral and topical NSAID/COX-2 inhibitors use
 - # Exclusion of study participants with a history of RPOA, osteonecrosis, SIF, avascular necrosis, and other significant arthropathies
 - # Exclusion of study participants with pre-existing clinically significant motor neuropathy
 - # Exclusion of participants with other medically significant or poorly controlled comorbidities, including significant cardiovascular disease (including Class 3 and Class 4 (NYHA 1994) heart failure)

- # Exclusion of participants with active infection and clinically important infection, including chronic, persistent, or recurrent infections or recent acute infections within 3 months prior to screening or between screening and randomisation
- # Screening for the identification and exclusion of participants with human immunodeficiency virus (HIV), hepatitis B virus (HBV), hepatitis C virus (HCV), or TB.
- # Exclusion of participants who are receiving disease-modifying antirheumatic drugs (DMARDs) and other immunosuppressants
- # Exclusion of participants with history of any underlying condition that predisposes participant to infections (such as splenectomy or primary or secondary immunodeficiency syndrome)
- # Exclusion of participants with a history of an opportunistic infection or who lived in areas with endemic fungal infections
- ∀ Clinical safety monitoring and assessment procedures conducted at appropriate intervals at specified clinic visits during the clinical study, specifically including:
 - # Complete physical examinations at appropriate frequencies
 - # Neurological examination, including peripheral nervous system examination with TNSn assessment at appropriate frequencies.
 - # Follow-up (FU) required for cases of suspected occurrence or worsening of neuropathy by neurologist and on protocol-prespecified cases of bradycardia, orthostatic hypotension, syncope, anhidrosis, or hypohidrosis by a neurologist and/or cardiologist (Section 8.2.2)

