 - # Baseline evaluation of left ventricular ejection fraction (LVEF) using echocardiography in cases of Class 1 and Class 2 (NYHA 1994) heart failure and follow-up on cases of suspected new occurrence or worsening of heart failure by cardiologist.
 - # Monitoring for AEs (including but not limited to evidence of infection, joint safety events, cancer, symptoms of neuropathy, and sympathetic autonomic dysfunction), vital signs (including orthostatic blood pressure [BP] measurements), ECGs, and safety laboratory tests (haematology, clinical chemistry including C-reactive protein (CRP), liver function tests, coagulation tests, and urinalysis) at appropriate frequencies
 - # Monitoring of concomitant medication use
 - # Monitoring for injection site reactions and hypersensitivity
 - # Use of appropriate imaging techniques (X-ray or magnetic resonance imaging [MRI]) for evaluation of protocol-prespecified major joints at relevant time points (including baseline and FU) and at any time point (in addition to protocol-prespecified joints), when clinically indicated (Section 8.2.6).

- ∀ Independent expert adjudication of suspected or confirmed cases of possible or probable joint safety events including but not limited to RPOA, SIF, primary osteonecrosis, or pathological fracture cases that are experienced by the study participants (Section 8.2.7 and Section 9.6).
- \forall Application of individual stopping criteria (Section 7.1.1)
- ∀ Unblinded Data and Safety Monitoring Board (DSMB) to review safety data (Section 9.6)

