 - # Or any other of psychiatric illness according to the criteria in the Diagnostic and Statistical Manual of Mental Disorders (fifth edition), if, in the opinion of the investigator, the psychiatric disorder or symptom is likely to confound interpretation of drug effect, affect pain assessment, or affect the participant's ability to complete the study
- 21 Significant cardiovascular disease including:
 - # Class 3 or Class 4 (NYHA 1994) heart failure (ejection fraction of < 40%) or clinically significant stenosis or occlusion of a carotid or vertebral artery
 - # Acute coronary syndrome/acute myocardial infarction, unstable angina, or coronary intervention with percutaneous coronary intervention or coronary artery bypass grafting within 6 months prior to screening
 - # High-degree AV block II-III, clinically significant sinus node dysfunction not treated with pacemaker, heart rate of \leq 45 beats per minute on screening ECG
 - # Ventricular or atrial arrhythmias requiring treatment. Participants with permanent atrial fibrillation and optimally regulated ventricular rate who are not on medication with an anticoagulant are eligible.
 - NOTE: Participants designated as NYHA functional Class 1 or Class 2 are not necessarily excluded from participation. However, such participants should have LVEF measured by echocardiography and documented at baseline.
- 22 Significant or chronic lung disease, including severe or unstable chronic obstructive pulmonary disease, severe or unstable asthma, current pneumonitis, or interstitial lung disease
- 23 Diabetes complicated with retinopathy (by history) or nephropathy. Uncomplicated, stable diabetes that is well controlled and actively managed is not exclusionary. Haemoglobin A1c levels above 8.5 are exclusionary.

- 24 Known or suspected systemic infection, including HIV, HBV, HCV, or TB should be excluded. If QuantiFERON test is positive at screening, participants will be excluded from the study except for the cases when the QuantiFERON test remains positive after the successful treatment of TB as confirmed and documented by the relevant specialist. Other tests could be performed if deemed necessary by the investigators to exclude systemic infection. Note: Positive results of hepatitis B surface antigen (HBsAg) or antibody to hepatitis B core antigen (anti-HBc) are exclusionary.
- 25 Participants with a history of an opportunistic infection or who lived in areas with endemic fungal infections

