- # Participants who have a proven diagnosis of sympathetic autonomic neuropathy
- # Development of malignancy
- # Development of Class 3 or Class 4 (NYHA 1994) heart failure
- # Positively-adjudicated possible or probable RPOA, SIF, primary osteonecrosis (including spontaneous osteonecrosis of the knee), or pathological fracture.
- # Participants who plan to undergo total joint replacement (knee, hip, or shoulder) or other arthroplasty procedure during the study
- # Haematologic toxicity, defined as one or more of the following:*
 - Leukocyte count $< 2.0 \times 10^9/L$
 - \circ Neutrophil count $< 1.0 \times 10^{9}/L$
 - \circ Platelet count < 75 × 10⁹/L
 - * Note: Participants must be advised to seek immediate medical attention if they develop any symptoms suggestive of blood dyscrasia or infection (eg,

persistent fever, sore throat, bruising, bleeding, or pallor). Haematology testing should be performed as soon as possible to exclude blood dyscrasia.

- # Development of a lupus-like syndrome, autoimmune hepatitis, or immune-complex disease
- # Development of COVID-19 infection that meets moderate or severe severity AE criteria.
- # Treatment with anti-SARS-CoV-2 monoclonal antibodies for COVID-19 infection of any severity.
- # Mild or asymptomatic COVID-19 infection with symptoms that have not resolved within 28 days since the last IP administration or results of appropriate testing for COVID-19 infection (ie, antigen-based) suggesting that a participant is carrying a replicating virus and remains positive within 28 days since the last IP administration.
- # There are other ongoing sequelae from COVID-19 infection, or the participant requires treatment for the manifestations of COVID-19 infection for the period beyond 28 days since the previous IP administration, or less than 5 half-lives have passed since the last COVID-19 antiviral medications administration within the 28-day period since the last IP administration.
- # If per investigator's judgement, the amount of rescue medication taken by the participant poses a risk for the participant to continue safely in the study.

7.1.2 **Procedures for Early Discontinuation of Investigational Product**

A participant who discontinues IP early (ie, prior to receiving the last dose of IP) should always be asked about the reason(s) and the presence of any AEs. The reason for premature discontinuation of IP should be documented in the source documentation and recorded in the eCRF.

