7.1.3 Temporary Discontinuation of Investigational Product

Withholding IP administration temporarily may be considered in the following cases:

- ∀ Development of sensory abnormalities (eg, paraesthesia, dysesthesia, burning, pins and needles) to confirm their resolution within 14 days prior to the next IP administration
- ∀ AE suggestive of new occurrence or worsening of peripheral neuropathy
- ∀ Participants who have the following sympathetic function AEs (any seriousness or severity):
 - # Meet the prespecified criteria for bradycardia (Section 8.2.4)
 - # Meet the prespecified criteria for confirmed orthostatic hypotension (Section 8.2.3.2)
 - # Have syncope
 - # Report anhidrosis or hypohidrosis
- ∀ Cases where additional evaluation or adjudication is needed to exclude possible or probable RPOA, SIF, primary osteonecrosis (including spontaneous osteonecrosis of the knee), or pathological fracture.

- ∀ Cases of signs/symptoms suggestive of worsening or new occurrence of heart failure
- ∀ When follow-up on cases of abnormal liver function is needed before the decision on permanent IP discontinuation is made (eg, identification of potential HL (PHL) cases needed or further evaluation in order to exclude HL required, or ALT or AST ≥ 5 × ULN for less than 2 weeks)
- \forall A positive test for SARS-CoV-2 at any time point during participation in the study.
- ∀ Symptoms or signs consistent with COVID-19 infection (eg, fever, cough, dyspnoea), confirmed by an appropriate laboratory test.

Participants who meet criteria for bradycardia, orthostatic hypotension, who have had a syncope, or report anhidrosis or hypohidrosis should be evaluated by a cardiologist or neurologist as soon as possible.

Participants with AEs suggestive of new occurrence or worsening of peripheral neuropathy as per investigator's neurological assessment should be evaluated by a neurologist as soon as possible.

Participants with clinical signs/symptoms suggestive of worsening or new occurrence of heart failure should be evaluated by a cardiologist as soon as possible. Echocardiography should be performed if clinically indicated. The participant should not be dosed with the subsequent dose of IP until (if applicable) the absence of sensory abnormalities, sympathetic dysfunction, new occurrence or worsening of peripheral neuropathy or Class 3 or Class 4 (NYHA 1994) heart failure have been confirmed, or RPOA, SIF, primary osteonecrosis, or pathological fracture have been excluded.

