8.2.1 Physical Examinations

A physical examination will be performed and include assessments of the following: general appearance, skin, head and neck, examination of the oral cavity for any lesions, lymph nodes, thyroid, abdomen (bowel sounds, liver, and spleen palpation), back (including costovertebral angle tenderness), musculoskeletal/extremities, cardiovascular, and respiratory systems.

If clinical signs/symptoms suggestive of worsening or new occurrence of heart failure are noted, a consultation with a cardiologist should be obtained as soon as possible. Echocardiography should be performed if clinically indicated. Participants designated as NYHA functional Class 1 or Class 2 should have LVEF measured by echocardiography and documented at baseline.

The participant should not be dosed with the subsequent dose of IP until the absence of Class 3 or Class 4 (NYHA 1994) heart failure has been confirmed (refer to the Section 7.1.3).

Height and weight will be measured at screening and weight at the Week 12 visit. Weight should also be measured when change is suspected or fluid retention occurs.

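### Exclusion criterion 21 attaches an ejection-fraction limit to Class 3-4 heart failure that the risk plan, stopping rule and dosing holds do not carry

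*Protocol*

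**What the plan says.** Criterion 21 (Protocol 5.2) lists significant cardiovascular disease as exclusionary. Its first bullet reads "Class 3 or Class 4 (NYHA 1994) heart failure (ejection fraction of < 40"%), followed by carotid or vertebral artery disease. A NOTE under the same criterion adds: "Participants designated as NYHA functional Class 1 or Class 2 are not necessarily excluded from participation". It continues: "However, such participants should have LVEF measured by echocardiography and documented at baseline".

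The other current mentions of Class 3-4 heart failure are these:

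- **Risk plan, 2.3.1.4.** Among the exclusions it names participants with serious or poorly controlled comorbidity, "including significant cardiovascular disease (including Class 3 and Class 4 (NYHA 1994) heart failure").
- **Permanent discontinuation, 7.1.1.** "Development of Class 3 or Class 4 (NYHA 1994) heart failure" stops further dosing.
- **Release of a held dose, 7.1.3.** No further dose is given until the absence of several conditions is established, among them "new occurrence or worsening of peripheral neuropathy or Class 3 or Class 4 (NYHA 1994) heart failure have been confirmed".
- **Release of a held dose, 8.2.1.** The next dose waits "until the absence of Class 3 or Class 4 (NYHA 1994) heart failure has been confirmed".

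On measurement, 2.3.1.4 calls for "Baseline evaluation of left ventricular ejection fraction (LVEF) using echocardiography in cases of Class 1 and Class 2 (NYHA 1994) heart failure". The criterion 21 NOTE and section 8.2.1 repeat that requirement for Class 1 or 2. The only other echocardiography instruction, in 7.1.3 and 8.2.1, applies when heart failure is newly suspected or worsening. It is left to clinical indication and has no cut-off.

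**The concern.** The criterion that sites apply at entry reads as narrower than the safeguard it is meant to deliver. If the parenthesis is a second condition, a patient in Class 3 or 4 with an ejection fraction of 40% or more does not meet the bullet, although 2.3.1.4 says such a patient is excluded. Nothing the protocol requires would show on which side of 40% a Class 3-4 patient falls.

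The subject matters for this drug. MEDI7352 binds TNF, and section 2.3.1.1 lists new or worsening congestive heart failure among the etanercept warnings. Keeping Class 3-4 patients out is one of the protocol's own named mitigations. Section 5 allows no waivers from the entry criteria, so sites in several countries should not have to reconcile the criterion with a background section before applying it.

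**Working it through.** No formula applies. The check is a comparison of every place in the current text, leaving out the amendment history, that names Class 3-4 heart failure or requires a left ventricular ejection fraction (LVEF).

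**Mentions of Class 3-4 heart failure**

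| Section | Function | LVEF limit |
|---|---|---|
| 2.3.1.4 | Risk plan: exclusion | None |
| 5.2, criterion 21 | Entry criterion | Below 40% |
| 7.1.1 | Permanent stop | None |
| 7.1.3 | Release of held dose | None |
| 8.2.1 | Release of held dose | None |

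Total 5; with a limit 1; without a limit 5 − 1 = 4. Only 2.3.1.4 against criterion 21 compares like with like, since both concern entry. The other three are on-treatment rules. They show that elsewhere the protocol treats class alone as the bar to dosing.

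**Baseline LVEF requirements**

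| Section | Applies to |
|---|---|
| 2.3.1.4 | Class 1 and 2 |
| 5.2, criterion 21 NOTE | Class 1 or 2 |
| 8.2.1 | Class 1 or 2 |

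Total 3; covering Class 3-4, 0. This is one requirement stated three times.

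**Testing the two readings of the parenthesis**

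1. *It is a second condition.* The excluded set is then Class 3-4 with LVEF below 40%, which is smaller than the set in 2.3.1.4. The difference is Class 3-4 with LVEF of 40% or more. Applying the limit needs an LVEF in Class 3-4, which the protocol does not require.
2. *It is a gloss on what Class 3-4 means.* The excluded set then agrees with 2.3.1.4 and no LVEF is needed. But the NOTE itself describes the NYHA grading as functional, so an ejection fraction does not define it. Criteria 43 and 44 use a parenthesis in the same way to give an operative numerical definition, which makes the limiting reading a natural one.

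The first reading contradicts the risk plan; the second leaves words that do no work and can mislead.

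**Would a later rule catch the gap?** The stop in 7.1.1 acts on the development of Class 3 or 4. The hold in 7.1.3 is triggered by signs of new or worsening heart failure. Neither is worded for stable Class 3-4 disease already present at entry. If such a participant worsened, dosing could resume only once Class 3-4 was shown to be absent. These rules therefore presuppose that nobody enters in Class 3 or 4.

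**The case against.** The case against is that the context already settles the matter. Criterion 21 opens with a non-exhaustive list. Its NOTE leaves room only for Class 1 or 2, which implies that Class 3-4 is out. Criterion 15 (not suitable for joint replacement), criterion 32 (serious or unstable illness) and criterion 42 (important abnormality at screening) give further grounds to exclude. A protocol that excluded all Class 3-4 patients would ask for LVEF only in Class 1-2, so the absence of that measurement in Class 3-4 supports the gloss reading. The on-treatment rules need not share the entry threshold. Finally, deleting the parenthesis removes the only LVEF value in the protocol, and leaves the Class 1-2 echocardiogram with no figure to be judged against.

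Much of this stands. The intent to exclude all Class 3-4 is clear, the like-for-like conflict is a single pair of passages, and the missing LVEF matters only if the limit is a real condition.

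Two things do not follow. Criteria 15, 32 and 42 rest on the investigator's judgement, whereas 2.3.1.4 states a categorical exclusion. And clear intent is a reason to remove the conflicting words. The loss of the 40% figure costs no exclusion: Class 3-4 patients below 40% stay excluded by class, and the bullet never applied the figure to Class 1-2.

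**Conclusion.** The concern holds as a minor inconsistency in eligibility wording. Criterion 21 is the only one of five current mentions that limits Class 3-4 heart failure by ejection fraction. On its literal reading it is narrower than the mitigation in 2.3.1.4, and the protocol's required measurements could not apply the limit.

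No participant is shown to have been enrolled through this wording. The protocol gives no figure from which to estimate how many could be, and the number is zero if sites read the bullet as 2.3.1.4 does. Sample size, power and type I error are unaffected. The conclusion assumes that 2.3.1.4 expresses the sponsor's intent, which the criterion 21 NOTE supports. The wording should be corrected because it states an entry safeguard for a TNF-binding drug.

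**What to change.** In criterion 21, delete the parenthesis giving the ejection-fraction limit, so that the bullet names NYHA Class 3 or Class 4 heart failure without qualification, as 2.3.1.4 does. Leave the arterial part of the bullet, the remaining bullets and the NOTE unchanged.

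If the sponsor also wants a low ejection fraction to be exclusionary in its own right, that should be a separate line. The baseline echocardiogram already required in Class 1-2 could then enforce it. That would be a new exclusion and is not needed to resolve the inconsistency.

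The cost of the deletion is one line of wording and a short note to sites, with no added assessment.

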5.3 Lifestyle and Activity Considerations

Participants should maintain their daily normal routine including stable doses of permitted medication. Participants are also permitted to continue their nonpharmacologic activities interventions during the clinical study. Participants participating in a regular prescribed physiotherapy programme should maintain this for the duration of their participation in the study. Participants should be cautioned against performing strenuous exercise regimens during the study as it may influence laboratory results and pain data. Participants may participate in light exercise and recreational activities during the study.

Participants participating in a regular homeopathy or naturopathy programme should maintain this for the duration of their participation in the study.

Refer to Section 6.5 for guidance on permitted and prohibited medications.

5.3.1 Meals and Dietary Restrictions

Participants will be asked to avoid foods containing poppy seeds for 5 days prior to the screening visit.

Participants will be asked to avoid any changes in OTC products and herbals, vitamins, and minerals from at least 14 days prior to the first IP administration on Day 1 through to the end of the FU period. If needed, a nasal spray for nasal congestion may be used occasionally. If a change in concomitant medication is needed, the investigator must decide if the participant should remain in the study or be dismissed from the study. Procedures for early discontinuation of IP are provided in Section 7.1.2.

5.3.2 Tobacco Restrictions

Participants who use nicotine patches may continue to use them at the same dose and at the same time of day and must keep their smoking habit unchanged until at least Week 18 of the study. Although no change in smoking habits is preferred, smokers are permitted to quit smoking during the study. The investigator should be consulted, and the conversation documented in the participant's chart.

5.3.3 Other Restrictions

Participants must refrain from blood and plasma donation during the study and for at least 2 months after the final FU visit.

Fertile male participants must use appropriate contraception and must refrain from sperm donation from first dosing on Day 1 until at least 3 months and 20 days after the last dose of IP (Section 8.3.10).

5.4 Screen Failures

Screen failures are defined as participants who consent to participate in the clinical study but are not subsequently entered in the study because they do not meet the eligibility criteria for participation in this trial (screen failure) due to, but not limited to, the following criteria: a laboratory result, test result, consent withdrawal, pain severity, disallowed medication, or other reversible condition. A minimal set of screen failure information is required to ensure transparent reporting of screen failure participants to meet the Consolidated Standards of Reporting Trials publishing requirements and to respond to queries from regulatory authorities. Minimal information includes demography, screen failure details, eligibility criteria, and any SAE.

Individuals who do not meet the criteria for participation in this study (screen failure) may be rescreened once at the discretion of the investigator. Rescreening procedures are described below.

5.4.1 Rescreening

One rescreening attempt is permitted for each participant.

For the participants who have undergone X-ray assessments during the screening period (and provided that there were no triggering events [eg, trauma] affecting the joints or any clinically significant changes in joint condition since the X-ray evaluation during the screening period based on the investigator's assessment), then rescreening, if deemed necessary, must occur within 90 days from this first screening X-ray assessment. If it is not possible to assess such changes in clinical condition over the above-mentioned period, then the participants should not be rescreened. Note: There is no rescreening option beyond the above-mentioned 90 days for participants who have been exposed to X-rays during screening.

For the study participants who were considered screen failures before any X-ray images were obtained, one rescreening attempt is allowed at any time point while the study is ongoing.

All screening procedures and assessments (except for X-ray/MRI if performed at screening) should be repeated for the rescreened participants. A participant should sign a new ICF if they are to rescreened for any reason.

